Study Number: 1 R34 DA043784-01A1

Date: July 19, 2018

15) Risks to Subjects*

This study involves minimal risks with no prospect of benefit. We do not anticipate any adverse effects. Nevertheless, if a serious adverse event occurs, it will be reported to the Institutional Review Board (IRB). Risks related to study procedures will be monitored closely, and any changes to increase safety will be addressed. Risks identified as possible outcomes for all of our study subjects participating in the assessment:

- 1) possible violation of confidentiality,
- 2) possible discomfort due to assessment procedures,
- 3) possible psychological stress associated with discussing issues related to stigma and disclosing sensitive personal information,
- 4) possible disclosure of information about health status or abuse that would need to be reported to families and/or the appropriate agencies and ensuing investigation of the allegation(s) and further action, as indicated,
- 5) possible dissatisfaction with the assessment procedures, and
- 6) possible dissatisfaction with the intervention activities.

In addition, sensitive information about the participants may constitute a serious risk, as the information in essence will consist on records of delinquency, drug possession or serious first offense.

16) Potential Benefits to Subjects*

Potential Risks and Benefits There are several risks associated with this study. Potential breach of confidentiality, feelings of discomfort about sensitive information shared during interviews, focus group discussions and during therapeutic interventions. Some participants may experience psychological distress when questioned about risky behaviors associated with drug use and sexual activity, among others.

This research will develop and implement a culturally specific, family-based individual-based, sexual risk and delinquency risk reduction program for Haitian adolescents ages 13-17 in Miami-Dade County, Florida. As there are no documented interventions that have been specifically modified or created for this distinct cultural group, this preventive/intervention program could eventually allow clinicians to offer family-based interventions that integrate individually-oriented approaches to therapy and are better suited to the Haitian American sociocultural context.

Study Protocol

IRB ID: 20180597 (CR00012479)

Study Number: 1 R34 DA043784-01A1

Date: July 19, 2018

17) Vulnerable Populations*

. The youths to be recruited are minors aged 13-17.

18) Multi-Site Research*

This is not a Multi-Site Research.

19) Community-Based Participatory Research*

This study is not a Community-Based Participatory Research

20) Sharing of Results with Subjects*

Not Applicable.

21) Setting

When a youth is arrested in Miami-Dade, he or she is brought by the arresting officer to the JSD. At the JSD the child goes through an initial arrest process, including fingerprinting, mug shots and other typical intake and assessment procedures. During the intake the youths are asked to self-identify as to their ethnicity. The child is given an assessment which includes a determination of whether or not the appropriate criterion is met for entering a diversion program. Criteria for the various diversionary programs include prior criminal history and the nature of the current arrest. If the child is eligible for a diversionary program then the range and type of programs and services which might be suitable are considered. Programs are offered for substance abuse, educational needs, psychotherapy, family-based interventions, anger management, community service and so forth. If the parents and the youth both agree, then a diversion program is assigned.

Once assignment to a diversion program has been made, participation by the youth, and in many cases also by a parent, becomes a mandatory condition of the program. A case manager is assigned to monitor program compliance. If either fails to participate the program will not be completed and the youth may then be referred to the court system and may face prosecution and further sanctions.

When parents/guardians picking up a project eligible youth meet or when project staff meet eligible youth at the community diversion program, only then will they be informed about their eligibility of the proposed project. Parents/guardians and youths who are interested in participating in the project will then be informed that project services are provided in-home, confidential, and that participation is voluntary. Project's procedures will be performed at the home of the participants in the Haitian neighborhood in Miami-Dade.

22) Resources Available

The PI and Co-Investigators have each at least more than 30 years of large-scale experiences in the field of public health. They have over 3 decades of community-

Study Protocol

IRB ID: 20180597 (CR00012479)

Study Number: 1 R34 DA043784-01A1

Date: July 19, 2018

based research in the Haitian community in Miami-Dade. All research clinical staffs have been performing CIFFTA in diverse ethnic contexts in Miami-Dade for over two decades. They are well-trained in human subject protection and research implementation. They are well-informed of their tasks and duties and they will be trained for this study to be implemented in the Haitian community. The 88 at-risk youth (ages 13-16) of Haitian descent will be recruited in Miami-Dade County with the intention to analyze 80 participants because of attrition. Sample sizes are derived from power calculations based on data from published work.

Two therapists will deliver the CIFFTA intervention. Therapist will have experience in working with adolescents with behavior problems and with Haitian families. The first phase of therapist CIFFTA training will consist of a 3-day training workshop that includes the use of didactic material, the intervention manual, and the presentation of videotaped sessions from our previous CIFFTA work. This workshop will also include presentations by the PI and [name] on what is known about Haitian families in our community. The second phase will include intervention implementation with 1 pilot case. A therapist is required to work with a pilot case over at least a one-month period and work with that pilot cases will be supervised directly by the study PI, the CIFFTA Developer, and the CIFFTA supervisor. Because the implementation of the psycho-educational modules is fairly straightforward, training and certification efforts will focus primarily on the individual and family-based therapy components. Any rating below "adequacy" will require retraining on that specific component.

Interventions will be delivered over a briefer period than is typical of the actual intervention in the trial but will be sufficient to ensure comfort and competence in the key intervention components. There will be a 2 day workshop following the pilot phase to solidify any issues that remain and to incorporate any manual clarification that will assist in achieving high levels of competence and fidelity/adherence. This training format has been utilized successfully in our family training institute. SOC therapists will already be experienced in delivering the community standard and will not require additional training.

Intervention Integrity/Fidelity Checks: Weekly clinical meetings will be held to supervise the team. Each therapist will receive formal supervision in these meetings, in addition to consults as needed. Recorded therapy sessions will be reviewed, the clinical complexity of cases will be discussed, and good manual implementation will be emphasized. An independent adherence rater will randomly select 20% of the sessions at different intervention phases (early, mid, and late) for adherence ratings to document the adequacy of intervention delivery. Ratings that fall below adequacy on any dimension/component will trigger increased supervision focus for that dimension and if necessary, re-training. Adherence raters will be trained using the established CIFFTA adherence checklist. The condition supervisor will be held as the gold-standard for inter-rater reliability on adherence ratings and raters will be trained to achieve an intra-class

Study Protocol

IRB ID: 20180597 (CR00012479)

Study Number: 1 R34 DA043784-01A1

Date: July 19, 2018

correlation coefficient of .70 or higher, and at least 80% agreement across items. Inter-rater reliability will be checked regularly to avoid drift.

23) Prior Approvals

There was no prior approval.

24) Recruitment Methods

This project's approach will consist of the following steps: (a) after initial referral by the JSD, potential participants will be approached by the ethnographer who will describe the scope of the study and ask the participant if she or he wants to be enrolled. If the participant agrees, his/her family will be contacted. Once a family is contacted, the ethnographer will schedule the first home visit with the parent(s)/caretaker(s) of the potential participant. S/he will explain (a) the objectives of the study, (b) the possible recruitment of the youth under his/her care as well as their own participation, (c) the possible risks that this participation could involve (see Human Subjects), and (d) the content of the parental consent form. If the parent(s) of the potential participant express(es) interest in the study, the ethnographer will explain the study to the potential participant. The procedure for introducing the study to potential participants and their caretakers will be written in English and Haitian Creole. After obtaining the verbal agreement of the parent/caretaker and the verbal assent of the participant, ethnographer will recruit the participant and his/her parent(s) or caretaker(s). S/he will explain in detail the adolescent assent form and obtain the participant's signature (as well as the parent consent form) prior to any further activity related to the study. The ethnographer and each participant will then schedule a time and a place for the baseline interview. The baseline questionnaire that addresses questions of demographics, family structure, immigration, neighborhood context and risky behaviors will be administered to participants at baseline at the participant's home. The ethnographer, who will have received specialized training in the conduct of structured interviews, will conduct the baseline interviews. Each interview is expected to take 1-2 hours; participants will be offered \$50 for their time. At this point, the interventionist will contact the participant and her/his parent/caretaker to schedule the first intervention session. Subsequent contact between the interventionist and the participant will be once a week on a pre-scheduled appointment basis.

25) Local Number of Subjects

88

26) Confidentiality

Participants' contact information will be entered into the confidential password-protected tracking system. Their study information, however, will be de-identified in a separate file. If at the time of assent, consent or if it has been determined later

Study Protocol

IRB ID: 20180597 (CR00012479)

Study Number: 1 R34 DA043784-01A1

Date: July 19, 2018

that a participant is no longer eligible, the participant will be discontinued from the study and told that the study inclusion criteria are no longer met. All information regarding that participant will be destroyed. Every precaution will be taken to prevent any violations of confidentiality. Confidentiality of subject records is assured by assigning the participants research numbers and storing computer files without identifying information. A single password-protected file with identifying information will be kept for tracking purposes only. Only [name], [name] and the Postdoc will have access to the password protected files. All personal information and data contained in computer systems will be password-protected and stored in locked facilities. Paper records are kept in locked file drawers in a locked room.

This study will have an extended NIDA Certificate of Confidentiality to protect the subjects' confidentiality.

27) Provisions to Protect the Privacy Interests of Subjects

Parents/guardians and youths who are interested in participating in the project will be informed that project services are provided in-home, confidential, and that participation is voluntary. Interviews will be done at a comfortable place chosen by the study participant where there is no intrusion from a third party and where participant feel safe providing response to questions, examinations, and procedures.

Trained research staff will ensure participants of the study that all information regarding that participant will be destroyed and that every precaution will be taken to prevent any violations of confidentiality. Confidentiality of subject records is assured by assigning the participants research numbers and storing computer files without identifying information.

28) Compensation for Research-Related Injury

Not applicable.

29) Economic Burden to Subjects

There is no cost to participate in this study.

Consent Process

We will obtain signed assent from children participating in this research study as it is appropriate for the age, maturity and psychological state of the child. The consent/assent process will occur in the youths' homes by appointment, after they and their parents/guardians have left the Juvenile Services Department/Juvenile Assessment Center. Parents/guardians and youths will be informed that participation in the study is completely voluntary.

Non-English Speaking Subjects

Study Protocol

IRB ID: 20180597 (CR00012479)

Study Number: 1 R34 DA043784-01A1

Date: July 19, 2018

Although Haitian youths in this study are bilingual, their parents are most likely to be Creole speakers. The consent and assent forms will be translated in Haitian Creole and the process will be done in the language parents or youth is most comfortable with.

Waiver or Alteration of Consent Process (consent will not be obtained, required information will not be disclosed, or the research involves deception)

We will not apply for waiver in this study.

Cognitively Impaired Adults

No cognitively impaired individuals will be enrolled in this study.

Adults Unable to Consent

Not applicable.

30) Process to Document Consent in Writing

Informed consent attached.

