Study Protocol

IRB ID: 20180597 (CR00012479)

Study Number: 1 R34 DA043784-01A1

Date: July 19, 2018

Study Title

Culturally Modified Family Based Therapy for Haitian Youth in South Florida
(CIFFTA).

NCT number: 03876171

Date: July 19, 2018

INSTRUCTIONS:

1) Protocol Title

Culturally Modified Family Based Therapy for Haitian Youth in South Florida (CIFFTA).

2) IRB Review History*

None

3) Objectives*

The study will pursue the following Specific Aims:

Aim 1. To adapt CIFFTA and the assessment instruments necessary to test its efficacy to the unique Haitian sociocultural contexts. This process of adaptation has the purpose of optimizing CIFFTA's acceptability and cultural appropriateness. It will rely on ethnographic methods (participant observations, focus groups, and interviews) to guide the adaptation process.

Aim 2. Determine, via a pilot efficacy trial, the impact of CIFFTA compared with standard-of-care for reduction of drug use, risky sexual behaviors, and delinquency risk among Haitian adolescents ages 13 to 17 in Miami-Dade County. The ethnographic component of the study will monitor the delivery of the intervention, collecting process data, and affording the investigators needed perspective on the intervention's impact.

Aim 3. To generate preliminary data on the usefulness of assessment tools and CIFFTA's efficacy among the population. These data will help evaluate the effect of the intervention and its best form of implementation. They will also provide preliminary evidence to justify a full clinical trial of CIFFTA in a population of at-risk Haitian youth.

Primary study outcomes include: intervention attendance and completion; sustained abstinence in substance use through biochemical verification and self-report; family functioning; sexual risk behavior; and conduct disorder. Secondary outcomes include: recidivism in delinquency, improvement in family communication, and peer/gang involvement. Outcomes will be assessed through follow-up instruments at three points: 3, 6 and 12 months.

4) Background*

Despite preventive efforts made over the last three decades, it is clear that some populations have not benefited from attempts to deter them from risky behaviors. Haitian youth constitute an important but understudied population who may be particularly

Study Protocol

IRB ID: 20180597 (CR00012479)

Study Number: 1 R34 DA043784-01A1

Date: July 19, 2018

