Eighty-eight (88) adolescents aged 13 to17 and their families will be recruited into the study to obtain 80 after attrition. Age, place of residence (Miami-Dade), and Haitian ancestry will constitute the main criteria for selection. Other criteria of inclusion are: adolescents that are NOT incarcerated and with no prior mental health care or history of psychoactive medication, to increase the homogeneity of the sample in terms of a naive population; adolescents in families who have lived in the US for 3 years, to avoid confounding initial culture shock with other conventional aspects of maladjustment; families with a range of organizational structures (nuclear and non-nuclear), to achieve variability and observe differences in family dynamics with regard to response to the intervention. Youths with a documented history of mental retardation and/or organic dysfunction will be excluded; the youths in question will be referred to appropriate agencies.

6) Number of Subjects*

Eighty-eight (88) participants will be recruited into the study. Instruments for the intervention will be pretested with 10 Haitian youth.

7) Study-Wide Recruitment Methods*

This project’s recruitment approach will consist of the following steps: (a) after initial referral by the JSD, potential participants will be approached by the ethnographer who will describe the scope of the study and ask the participant if

Study Protocol

IRB ID: 20180597 (CR00012479)

Study Number: 1 R34 DA043784-01A1

Date: July 19, 2018

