school, criminal friends, alcohol/drug use, leisure/recreation, personality/behavior, family circumstances, and attitudes/orientation) yielding overall risk scores ranging from (0-8). The YLS/CMI is administered to all juveniles processed in the JSD. The same instruments will be used to assess youth from the GRP.

Drug use and psychological adjustment will be assessed with the Comprehensive Adolescent Severity Inventory developed by Myers and colleagues (52). The CASI covers a broad range of psychosocial and risk behaviors including information on substance abuse (e.g. age of first use, current patterns of use, friends' use), criminal activity, mental health, peer relationships, family/household relationships, education, and sexual behavior. Among other things, the instrument gathers information concerning youth use of a range of substances and will be adapted to assess ATOD use at baseline and post-intervention. In this way, we will be able to determine participants' historical and recent use (i.e. past 30 days, past 3, 6, and 12 months), if any, of drugs and alcohol. Similar assessments are made of sexual risk behavior and a global assessment of psychological adjustment is included that yields a continuous measure of global functioning. Adequate levels of internal consistency, test-retest reliability and validity coefficients are reported.

Conduct Disorder. Youth problem behaviors will be measured using the Conduct Disorder instrument from a Revised Behavior Problem Checklist (53) utilized previously by BSFT staff (54). The RBPC is an empirically derived measure consisting of 89 problem behaviors. We will adapt the instrument to include behaviors that are particularly salient among Haitian youths and exclude others that are deemed less salient. For each youth, the primary caregivers will rate the severity of each behavior on a 3 point scale (0 = no problem, 1 = mild problem, 2 = severe problem). The Conduct Disorder Subscale as used for this study consists of 22 items ($\alpha = .92$) measuring the youth's disruptive behavior at home (e.g., "disobedient; difficult to control"). The Conduct Disorder Subscale will be administered at intake and again at termination.

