difference at a particular time between the two conditions (6). Following Cohen's guidelines (5), we will interpret our effect sizes using the convention of "small" ( $d = .2$ ), "medium" ( $d = .5$ ), and "large" ( $d = .8$ ).

Our hypotheses concerning the direct and indirect effects of key variables on drugs/alcohol use, risky sexual behavior, delinquent behavior, and recidivism will be tested using SEM mediation analyses. To test potential indirect relationships we will include several mediators, including family connectedness, acculturation (bicultural involvement scale), and motivation to change. This will allow us to examine whether CIFFTA directly effects our outcomes of interest and/or whether the effect of CIFFTA operates through its effect on family connectedness, acculturation, and motivation to change. These mediation models will enable us to address **Specific Aim #2** by testing the significance of paths in the model linking the intervention variable to the risk-related outcomes in question (both at discrete points in time and as the change index derived from differences in ordinal frequency at baseline and at post-intervention time intervals).

In a separate set of analyses, we will examine the hazard rate of drug/alcohol use and sexual risk behavior during the post-intervention phase of the study. Comparisons across the two intervention conditions will thus be made regarding the hazard rate of having sex during the post-intervention period, sex with multiple partners ( $>1$  per month), and unprotected sexual episodes. Specifically, shared frailty Cox proportional hazard regression will be utilized to examine possible differences in the hazard rate of various risky behaviors (drug- and sex-related) in CIFFTA and control conditions during the post-intervention phase. This will prove particularly helpful in determining the hazard rate for post-intervention sexual initiation or unprotected sex in the two groups being compared, while also controlling for the time-dependence nature of our data. Similar analyses will be performed regarding initiation into drug use and other problem behaviors to determine whether the possible benefits of the CIFFTA approach extend to a range of risky behaviors.

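### The abstinence outcome and the post-intervention hazards of use and sex carry no baseline-status term or risk set, although eligibility admits users and non-users alike

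*Protocol*

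**What the plan says.** **Who enters.** Protocol section 5 says "Age, place of residence (Miami-Dade), and Haitian ancestry will constitute the main criteria for selection". It adds not being incarcerated, no prior mental health care or psychoactive medication, and three years of family residence in the US. Youths come through the juvenile diversion programme, for which section 21 says "Criteria for the various diversionary programs include prior criminal history and the nature of the current arrest". Neither section asks for drug use or sexual activity.

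**What is asked.** Aim 2 (section 3) concerns the "impact of CIFFTA compared with standard-of-care for reduction of drug use, risky sexual behaviors, and delinquency risk among Haitian adolescents". Section 10 (Ethnography) also speaks of preventing drug use. A primary outcome in sections 3 and 9 is "sustained abstinence in substance use through biochemical verification and self-report". Neither document says how a youth who was not using at baseline counts on it, and the SAP names no model for it.

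**How the hazards are compared.** SAP, Analytic Methods: "we will examine the hazard rate of drug/alcohol use and sexual risk behavior during the post-intervention phase of the study". The comparisons by condition include "the hazard rate of having sex during the post-intervention period", multiple partners and unprotected episodes. The method is also put forward for "determining the hazard rate for post-intervention sexual initiation or unprotected sex in the two groups being compared", with similar analyses for initiation into drug use.

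**What is known at baseline.** With the CASI, section 10 says, "we will be able to determine participants' historical and recent use". Urine is also collected at baseline, and randomisation follows the logging of baseline data (section 10, Study Process). No stratification by baseline use or sexual activity is stated.

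**The concern.** Whether a youth was using drugs or sexually active at entry is likely to be among the strongest predictors of doing so afterwards. Leaving it out of a hazard model or an abstinence comparison in 80 youths wastes information that the trial already holds.

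There is also a question of meaning. A youth who has never used and continues not to use is an abstinence success without any reduction. A user who stops is a success through reduction. Both outcomes interest this plan, but a single pooled proportion or hazard ratio cannot say which one moved.

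The initiation hazards have a related gap. Only a youth naive at baseline can initiate, yet no naive risk set is stated.

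**Working it through.** **The plan's own figures.** There is no power figure for the abstinence outcome or the hazards. The SAP's 0.84 to 0.86 refers to R² = 0.05 in a simple SEM with 80 youths. It is a separate matter and this point does not use it.

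**Inputs from the documents.** 80 analysed out of 88 recruited (SAP, Power Analysis), allocated 1:1 (11 per arm per wave, Protocol section 8), so 40 per arm.

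**Inputs assumed, because the documents give none.** Share of baseline users p from 30% to 70%; 12-month control risk of use in users r_u from 70% to 85% and in non-users r_n from 10% to 30%; hazard ratio (HR) 0.5 in both groups; two-sided 0.05.

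**Step 1: what the pooled abstinence figure contains.** Abstinence is p(1 − r_u) + (1 − p)(1 − r_n) in control. In the CIFFTA arm each survival term is raised to the power HR. With p = 0.5, r_u = 0.85, r_n = 0.20:

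- Control: 0.5 × 0.150 + 0.5 × 0.800 = 0.475.
- CIFFTA: 0.15^0.5 = 0.387 and 0.80^0.5 = 0.894, so 0.5 × 0.387 + 0.5 × 0.894 = 0.641.
- Difference: 0.641 − 0.475 = 0.166, or 17 points over all youths.
- In users: 0.387 − 0.150 = 0.237, or 24 points. In non-users: 0.894 − 0.800 = 0.094, or 9 points.
- Share of all abstainers who were baseline non-users: 0.5 × (0.800 + 0.894) / (0.475 + 0.641) = 0.847 / 1.116 = 76%.

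Over the assumed range the pooled difference is 11 to 21 points, against 24 to 25 in users and 5 to 14 in non-users. Non-users make up 44% to 88% of abstainers.

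**Step 2: why the pooled figure does not isolate reduction.** Fix the effect in users at 20% versus 50% abstinent (30 points), with half the youths users:

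- Non-users 85% in both arms: 0.5 × 0.50 + 0.5 × 0.85 − (0.5 × 0.20 + 0.5 × 0.85) = 0.675 − 0.525 = 15 points.
- Non-users 70% versus 90%: 0.5 × 0.50 + 0.5 × 0.90 − (0.5 × 0.20 + 0.5 × 0.70) = 0.700 − 0.450 = 25 points.

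The reduction in users is the same, but the pooled result is 15 or 25 points.

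**Step 3: power of the Cox comparison.** Exponential event times censored at 12 months, 40 per arm, HR 0.5 in both groups, 600 replicates, with and without one baseline-use covariate; an independent repeat is in brackets.

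| Setting | Without covariate | With covariate |
|---|---|---|
| 50% users, risks 85%/20% | 0.36 (0.35) | 0.55 (0.53) |
| 30% users, risks 80%/10% | 0.18 (0.19) | 0.32 (0.33) |
| Weakly prognostic, risks 70%/30% (repeat at 50% users) | 0.44 (0.42) | 0.48 (0.49) |

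The simulation standard error is about √(0.36 × 0.64 / 600) = 0.02. In the first setting the estimated HR moved from about 0.58 without the covariate to 0.49 with it. With no treatment effect in that setting, the unadjusted analysis rejected in about 5% of runs with a mean HR of 1.00. A separate null run rejected in about 4% with and without the covariate.

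**Step 4: chance imbalance.** The standard deviation of the difference in user share between arms is √(2p(1 − p)/40): √(0.50/40) = 0.112 at p = 0.5 and √(0.42/40) = 0.102 at p = 0.3 or 0.7, so 10 to 11 points.

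**The case against.** **The mixing is intended.** The protocol speaks of prevention as well as reduction, and the SAP plans initiation analyses, so non-users belong to the target population. This stands. A reader might infer that non-users have nothing to gain and merely dilute the effect. The documents do not support that, and in Step 1 non-users gain 5 to 14 points. The smaller pooled difference there reflects their lower risk, not failure to respond.

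**The comparison is valid as it is.** This also stands. Randomisation protects the all-youth comparison, and chance imbalance is already reflected in its standard error. Under a common effect, the move of the HR towards 1 is the difference between a marginal and a conditional hazard ratio (non-collapsibility). It is not bias.

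**The full trial is not sized from these analyses.** A reader might infer that a diluted effect would be carried into the next trial. SAP, Analytic Methods takes those effect sizes from the latent growth models, as Cohen's d for rate of change and for differences at a time point, and those models carry baseline as the intercept.

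**Silence is not exclusion.** The SAP gives no covariate list for the hazard models, so baseline status is unspecified, not ruled out. That is fair, and it is why the remedy is to specify it. The intercept and the zero-inflated option belong to the growth and count models. The shared frailty handles dependence of survival times and does not replace measured baseline use.

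**The gains are assumed and probably optimistic.** The simulation uses exact event times and an error-free covariate. The plan assesses at 3, 6 and 12 months and expects under-reporting (Protocol section 12). The SAP also calls its analyses preliminary. All of this limits the size claimed, not the direction.

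**Conclusion.** The point holds as one of precision and interpretation. Entry requires neither drug use nor sexual activity, the plan has both reduction and prevention in view, and neither document ties the abstinence outcome or the post-intervention hazards to baseline status. Pooled results would therefore not answer Aim 2's reduction question separately, and they give up power that the baseline data could supply.

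On the assumed rates the gain from one covariate runs from 0.04 (0.44 to 0.48) to 0.19 (0.36 to 0.55) in the settings shown. It depends on how prognostic baseline use proves to be. The documents give no user share or event rate, so no figure here is a forecast for this trial. The simulations concern drug use only; the same reasoning applies to sexual activity, but its size was not calculated. The point does not show a biased trial or an understated effect for the full trial.

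**What to change.** Before analysis, add to the SAP:

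1. Baseline status as a prespecified covariate in the abstinence comparison and in the hazard models for any drug/alcohol use, having sex, multiple partners and unprotected sex. For substance use: recent use on the CASI or a positive baseline urine. For the sexual outcomes: sexually active or not at baseline. The urine panel does not test for alcohol, so alcohol status rests on the CASI.
2. A risk set restricted to youths naive at baseline for the sexual-initiation and drug-initiation hazards. A baseline-ever covariate is constant in that set, so item 1 does not apply to them.
3. A descriptive report of abstinence by arm in two rows: cessation among baseline users, and continued non-use among baseline non-users.

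The cost is SAP text. Eligibility, visits, data collection and sample size are unchanged. The downside is that the two rows are small (with 50% users, 40 × 0.5 = 20 per arm in each) and should be read as descriptive.
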